### 6.1.4 Adverse Event Collection Period

All adverse events reported from the time of study drug administration until 70 days following discontinuation of study drug administration have elapsed will be collected, whether solicited or spontaneously reported by the subject. In addition, serious adverse events will be collected from the time the subject signed the study-specific informed consent. Adverse event information will be collected and recorded on the appropriate eCRFs.

[figure not shown]
Subjects will be contacted approximately 70 days following study drug discontinuation for an assessment of any new or ongoing AEs, except those subjects that continue on adalimumab therapy after the end of study participation. These subjects are not required to complete the 70-day follow-up and any new Adverse Events should be reported

through the mechanism used for all post-marketing adverse experiences. The 70-day follow-up phone call will be recorded in source document only and confirmation of the contact will be faxed to AbbVie ([Appendix J](#)).

All Adverse Events identified to AbbVie from the 70-day follow-up phone call will be collected as source data to be evaluated and reported ([Figure 3](#)). Thus, all SAEs and nonserious AEs as defined by AbbVie, reported during the 70-day follow-up phone call must be captured in the clinical database. The end of trial is the last subject contact, i.e., the 70-day follow-up call.

Adverse event information will be collected as shown in [Figure 3](#).

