11.2 Analysis of Adverse Events

11.2.1 Treatment-Emergent Adverse Events

Treatment-emergent AEs during Maintenance Study are defined as events that begin or worsen either on or after the first dose of the study drug and within 70 days after the last dose of the study drug.

The 70-day follow-up phone call will not be required for any subject that initiates commercial adalimumab.

An overview of treatment-emergent AEs, including AEs of special interest such as adverse events leading to death and adverse events leading to premature discontinuation, AEs by Medical Dictionary for Drug Regulatory Activities (MedDRA version 21.0 or later) preferred term and system organ class, AEs by maximum relationship to study drug, and AEs by maximum severity will be summarized by number and percent.

The number and percent of subjects experiencing treatment-emergent adverse events will be summarized for the following adverse event categories.

- Any treatment-emergent adverse event.
- Any treatment-emergent adverse event that was rated as possibly related to study drug by the investigator (Reasonable Possibility).
- Any treatment-emergent severe adverse event.
- Any treatment-emergent serious adverse event.
- Any treatment-emergent adverse event leading to discontinuation of study drug.
- Any treatment-emergent adverse event leading to death.
- Any treatment-emergent adverse event of special interest.
- Any Deaths

Treatment-emergent adverse events will be summarized as follows:

- Grouped by System Organ Class and Preferred Term.
- A by-subject listing will be provided.
- Grouped by System Organ Class, Preferred Term and Severity.
- Grouped by System Organ Class, Preferred Term and Relationship to Study Drug.
- Grouped by System Organ Class and Preferred Term with subject numbers.

In treatment-emergent AE tables, a subject who reports more than one treatment-emergent AE in different system organ classes will be counted only once in the overall total. A subject who reports two or more different preferred terms which are in the same SOC will be counted only once in the SOC total. A subject who reports more than one treatment AE with the same preferred term will be counted only once for that preferred term using the most extreme incident (i.e., most "severe" for the severity tables and most "related" for the relationship tables).

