6.0 Analysis Conventions

Definition of Induction Baseline

The Induction Baseline visit date is the date when the first dose of study drug is received and referred to as Day 1 or Week 0. If a subject has not taken any study drug during Induction Study, the randomization date will be used as Day 1. The Baseline value for a variable is defined as the last non-missing value on or before the date of the first dose of study drug.

Definition of Induction Final Observation

Final Observation in the 12-week double-blind Induction Study is defined as the last non-missing observation collected within 70 days following the last dose of study drug for

subjects who are not re-randomized nor enrolled in Study M14-347, and on or before the day of the first dose of study drug in the 44-week double-blind Maintenance Study for subjects who entered the Maintenance Study or the day of the first dose of study drug in Study M14-347 if the subjects are enrolled in Study M14-347. Of note, the efficacy, laboratory, and vital sign evaluations performed on the day of first dose of study drug in the double-blind Maintenance Study or Study M14-347 will be included in the efficacy and safety analyses for the Induction Study. AEs with onset on the date of the first dose of the Maintenance Study/M14-347 will be attributed to the Maintenance Study/M14-347.

Definition of Rx Days (Days Relative to the First Dose of Study Drug)

Rx Days are calculated for each time point of interest and it provides a quantitative measure of days between the event and the first dose date. That is, the Rx Day is calculated as the event date minus the date of first dose of study drug plus 1. The Rx Day will be a negative value when the time point of interest is prior to the date of first dose of study drug, and the Rx Day will be a positive value when the time point of interest is after the first dose date. By this calculation algorithm the first dose day is Rx Day 1, while the day prior to the date of first dose is defined as Rx Day -1 (there is no Rx Day 0). Rx Days are used to map actual study visits to the protocol specified study visits.

Dealing with Multiple Measurements Collected on the Same Day

For efficacy related analyses, if multiple measurements for a particular parameter are collected on the same day for the same subject, the average of those measurements will be used.

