Observed case analysis will be performed such that missing values will not be imputed. Subjects in whom the following CD-related systemic or rectal corticosteroids that were not being taken at Baseline and are initiated during the study or who have dosages of these medications increased to greater than the dose taken at Baseline will be censored for efficacy assessments (i.e., will be considered non-responders for categorical endpoints and the observed non-categorical assessments will be replaced by last non-missing values prior to censoring) from that point through the end of the study.

Imputation of Missing Dates

For Baseline, efficacy, and safety parameters, if the day and/or month are missing, the following conventions will be used to impute the missing dates:

- 01 for missing start day
- End of month for missing end day
- January 1st for missing start month
- December 31st for missing end month

Rule for CDAI Calculation

Up to 14 days of diary entries will be evaluated from the ePRO tool for the CDAI calculation for each visit. The diary entries on the days the subjects receive endoscopy preparation medications, the day of endoscopy procedure, and 2 days after endoscopy procedure will be excluded. For each CDAI subscore, the available scores from the most recent diary days (at least 4 days, up to 7 days) prior to actual day of the study visit will be summed, and then multiplied by the corresponding multiplier to get subtotal score. If available diary entries are fewer than 7 days, the subtotal score will be calculated as (summed total available score/number of days) \times 7 \times corresponding multiplier. The three subtotal scores that are based on ePRO (number of liquid/very soft stools, abdominal pain rating, and general well-being) will then be rounded to one decimal. The final CDAI is rounded to a whole number.

If a subject has less than 4 days of diary data, the total CDAI score will not be calculated and will be considered missing.

Sensitivity analyses will be performed to make use of all available data based on the above rule if more than 5% of subjects have less than 4 days of diary data.

Definition of Clinical Remission

CDAI < 150.

Definition of Clinical Response

Decrease in CDAI \geq 70 points from Baseline.

Definition of Enhanced Clinical Response

Decrease in CDAI \geq 100 points from Baseline.

Definition of Endoscopic Remission

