11.2 Analysis of Adverse Events

11.2.1 Treatment-Emergent Adverse Events

Treatment-emergent AEs during Induction Study are defined as events that begin or worsen either on or after the first dose of the study drug and within 70 days after the last dose of the study drug for subjects who do not participate in the OLE (Study M14-347) or Maintenance study, or until first dose of maintenance study drug, or until first dose of study drug in the OLE study if the subject who enrolled under Amendment #3 or earlier, is a study completer and is enrolled in the OLE.

The 70-day follow-up phone call will not be required for any subject that initiates commercial adalimumab.

An overview of treatment-emergent AEs, including AEs of special interest such as adverse events leading to death and adverse events leading to premature discontinuation, AEs by Medical Dictionary for Drug Regulatory Activities (MedDRA version 21.0 or later) preferred term and system organ class, AEs by maximum relationship to study drug, and AEs by maximum severity will be summarized by number and percent.

The number and percent of subjects experiencing treatment-emergent adverse events will be summarized for the following adverse event categories.

- Any treatment-emergent adverse event.
- Any treatment-emergent adverse event that was rated as possibly related to study drug by the investigator (Reasonable Possibility).
- Any treatment-emergent severe adverse event.
- Any treatment-emergent serious adverse event.
- Any treatment-emergent adverse event leading to discontinuation of study drug.
- Any treatment-emergent adverse event leading to death.
- Any treatment-emergent adverse event of special interest.
- Any Deaths

Treatment-emergent adverse events will be summarized as follows:

- Grouped by System Organ Class and Preferred Term.
- A by-subject listing will be provided.
- Grouped by System Organ Class, Preferred Term and Severity.
- Grouped by System Organ Class, Preferred Term and Relationship to Study Drug.
- Grouped by System Organ Class and Preferred Term with subject numbers.

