In treatment-emergent AE tables, a subject who reports more than one treatment-emergent AE in different system organ classes will be counted only once in the overall total. A subject who reports two or more different preferred terms which are in the same SOC will be counted only once in the SOC total. A subject who reports more than one treatment AE with the same preferred term will be counted only once for that preferred term using the most extreme incident (i.e., most "severe" for the severity tables and most "related" for the relationship tables).

Adverse events will also be summarized by maximum severity. If a subject has an adverse event with unknown severity, then the subject will be counted in the severity category of "unknown," even if the subject has another occurrence of the same adverse event with a severity present. The only exception is if the subject has another occurrence of the same adverse event with the most extreme severity – "Severe." In this case, the subject will be counted under the "Severe" category.

Adverse events will also be summarized by maximum relationship to study, as assessed by the investigator. If a subject has an adverse event with unknown relationship, then the subject will be counted in the relationship category of "unknown," even if the subject has another occurrence of the same adverse event with a relationship present. The only exception is if the subject has another occurrence of the same adverse event with a relationship assessment of "Reasonable Possibility." In this case, the subject will be counted under the "Reasonable Possibility" category, respectively.

Incidence rates per 100 patient years of exposure to study drug will be presented for AE overviews and for AEs by SOC and preferred term where the number of events will be used as the numerator.

All Adverse Events identified to AbbVie from the 70-day follow-up phone call will be collected as source data to be evaluated and reported. Thus, all SAEs and nonserious AEs as defined by AbbVie, reported during the 70-day follow-up phone call must be captured in the clinical database. The end of trial is the last subject contact, i.e., the 70-day follow-up call.

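### A missing AE start day is set to the 1st of the month with no check against first dose, so some on-treatment AEs in the month of first induction dose lose treatment-emergent status

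*SAP*

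**What the plan says.** The Induction SAP, section 6.0 (Imputation of Missing Dates), sets the scope of its rule as "For Baseline, efficacy, and safety parameters, if the day and/or month are missing", and the first convention is "01 for missing start day". A missing start month becomes 1 January. The Maintenance SAP, section 6.0, carries the same conventions. Protocol 8.1.5 names AEs among the primary safety parameters, so the rule reaches AE start dates.

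The Induction SAP, section 11.2.1, defines treatment-emergent AEs as "events that begin or worsen either on or after the first dose of the study drug", and the Maintenance SAP uses the same date test. The only rule that assigns an AE by onset date concerns the changeover to the next period: "AEs with onset on the date of the first dose of the Maintenance Study/M14-347 will be attributed to the Maintenance Study/M14-347". AE rates per 100 patient-years are computed "where the number of events will be used as the numerator".

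Protocol 6.1.4 sets the collection period: "All adverse events reported from the time of study drug administration" onward, with one exception, that "serious adverse events will be collected from the time the subject signed the study-specific informed consent".

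Neither SAP nor the protocol compares an imputed start date with first dose, and neither gives a default status to an AE with a partial start date.

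**The concern.** Treatment-emergent status is decided by date, and the imputation picks the earliest possible day in the month. For a subject first dosed mid-month, that day lies before dosing. An AE that began after dosing in the same month is then classed as pre-treatment. For a non-serious AE this contradicts the protocol's own collection rule, because such an AE is in the database only if it was reported from dosing onward.

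The wording on worsening does not rescue the event. Protocol 6.1.1.1 has worsening reported as a new AE, with its own start date. A subject may still be counted through another record of the same term, but the event rate uses the number of events, so each lost onset lowers it.

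At stake is the completeness of early treatment-emergent AE counts and rates in a trial whose primary objective covers safety as well as efficacy.

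**Working it through.** The documents give no figure for this rule, so there is none to reproduce. The check applies the rule as written.

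**Example.** First dose 10 June, true onset 20 June, day missing. Imputed start = 1 June. Since 1 June is before 10 June, the AE is not treatment-emergent. If first dose is 1 June, the imputed start equals the first-dose date, the on-or-after test is met, and the AE is kept.

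**Inputs.**
- Imputed start = day 1 of the onset month (both SAPs, section 6.0).
- An onset is lost if its imputed start is before first induction dose (Induction SAP 11.2.1).
- Induction window: Rx Days 1-84.
- Assumption: first-dose dates uniform over 2015-2018 (1,461 days), and onsets uniform over the window. The documents give neither distribution.

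**Enumeration of every first-dose date against every onset day.**

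| Onset window (Rx Days) | Date pairs | Lost | Share |
|---|---|---|---|
| 1-84 | 1,461 × 84 = 122,724 | 21,520 | 17.5% |
| 1-28 | 1,461 × 28 = 40,908 | 21,420 | 52.4% |
| 29-84 | 1,461 × 56 = 81,816 | 100 | 0.1% |
| 8-84 | 1,461 × 77 = 112,497 | 21,520 − 8,883 = 12,637 | 11.2% |
| 15-84 | 1,461 × 70 = 102,270 | 6,106 | 6.0% |

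**First-of-month exception.** Of onsets in the calendar month of first dose, 93.6% are lost and 6.4% are kept because first dose was on the 1st.

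**Overlap with the dosing contrast.** Both arms receive 160 mg at Baseline; the regimens first differ at the Week 1 dose, about Day 8 (Induction SAP 4.2). Lost onsets on Days 1-7 number 8,883, and 8,883 / 21,520 = 41.3%. The window that bears on the contrast is therefore Days 8-84.

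**From shares of partial dates to shares of all onsets.** The rate of partial dates is not given. I assume that 1% to 5% of AE start dates lack the day:
- Days 1-84: 1000 × (0.01 to 0.05) × 0.1754 = 1.8 to 8.8 per 1000 onsets.
- No partial dates in Week 1: 1000 × (0.01 to 0.05) × 0.1123 = 1.1 to 5.6.
- No partial dates in Weeks 1-2: 1000 × (0.01 to 0.05) × 0.0597 = 0.6 to 3.0.

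**After the fix.** Every lost day-missing onset lies in the month of first induction dose, so imputing the first-dose date there takes the loss to 0%.

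**Maintenance onsets.** With an 84-day induction and onsets uniform on maintenance Days 1-308, the present rule places 4.8% of day-missing maintenance onsets in induction and none before it. The fix leaves this unchanged.

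**Missing month.** Under the 1 January rule, 88.4% of induction onsets with a missing month are dated before first dose. Of maintenance onsets, 22.7% go to induction and 35.0% fall before induction, hence out of both periods. Flooring all of these at first induction dose would put 22.7% + 35.0% = 57.7% of month-missing maintenance onsets in induction.

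**The case against.** The strongest case is that the effect is negligible. Onset date is a required item (Protocol 6.1), the first dose is given on site (Protocol 5.3.1.1), and visits follow at Weeks 2 and 4. Protocol 11.0 provides source verification and checks for inconsistent dates, and Induction SAP 4.4 has discrepant data clarified before the lock. Serious AEs must be reported within 24 hours of site awareness (Protocol 6.1.1.2), and the Induction SAP tabulates all deaths separately from treatment-emergent AEs leading to death. What remains is mainly non-serious AEs with a poorly recalled day. AEs are summarised by number and percentage, with no planned hypothesis test. All of this stands, and it is why the severity is low. It does not change what the written rule does to the partial dates that survive cleaning.

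A reader might infer three stronger things, and the documents support none of them:
- **That 17.5% or 52.4% of early AEs are lost.** These are shares of AEs with a missing day, not of all AEs.
- **That the loss distorts the comparison of regimens.** The same rule applies in both arms and no between-arm bias is shown. About 41% of the lost onsets fall before the regimens differ.
- **That every partial date in the first-dose month is lost.** That is untrue when first dose is on the 1st.

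A further objection is that a floor at first dose admits truly pre-dose events. This also stands, and is counted as a cost under the fix.

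**Conclusion.** The rule is wrong as written. Followed literally, it classes some on-treatment AEs as pre-treatment, and nothing else in the protocol or either SAP repairs this. The effect is a small under-count of early treatment-emergent AEs and of event rates, always in the direction of fewer events. No effect on a co-primary or ranked endpoint is shown.

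The percentages rest on uniform first-dose dates and onsets, and the per-1000 figures also on the assumed 1% to 5% partial-date rate. Early dates are probably less often partial than later ones, which favours the lower figures. The mechanism is certain; its size is unknown and probably small. Low severity: a specification gap to close before programming, not a threat to the trial's conclusions.

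**What to change.** Add one sentence to section 6.0 of each SAP, for AE start dates only: when the day is missing and the known month and year are those of first induction dose, impute the first induction dose date, unless the end date shows that the event stopped earlier. Use this single imputed date in both SAPs, so that each AE falls in one period. Report the number of partial AE start dates by arm, so that readers can see the actual size.

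Do not extend this floor to dates with the month missing, since it would place most such maintenance onsets in induction (57.7% under the assumptions above). These should be rare; query them and list them.

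The cost is a standard programming rule and one side effect. Serious AEs are collected from consent, so some truly pre-dose ones may count as treatment-emergent. With uniform dates, 52.4% of day-missing serious onsets in the 28 days before dosing fall in the first-dose month (21,420 of 40,908 date pairs) and would move to first dose unless the end date rules them out. For a safety count that is the more cautious error.
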